# 7.5.4 Stable Disease

Patients who have not achieved a CR, or PR and who have not exhibited progressive disease, will be considered to have stable disease (which is equivalent to a nonresponse).

# 7.6 Correlative Studies

To support exploratory objectives and correlative studies, blood and bone marrow aspirate will be collected at the time points indicated on the Schedule of Events. After completion of the described correlative studies, any remaining blood or bone marrow aspirate will be stored for future unspecified cancer research. With the participant's approval and as approved by the Institutional Review Board (IRB), de-identified biological samples will be stored at Huntsman Cancer Institute's Biorepository.

At the time of consent, subjects will be given the opportunity to authorize the biobanking of their remaining samples for use in future undisclosed research. During the conduct of the study, an individual participant can choose to withdraw consent to have biological specimens stored for future research. However, the withdrawal of consent with regard to biosample storage may not be possible after the study is completed.

# 7.6.1 Peripheral Blood Samples For Correlatives

Up to 40mLof blood will be collected at the time points listed in the Schedule of Events. See the lab manual for collection, processing, and storage instructions.

# 7.6.1.1 Measurement of DNA Damage and Repair Markers

The peripheral blood specimens will be assessed for DNA damage by quantitation of  $\gamma$ H2AX and cleaved PARP1 in CD5+/CD19+ cells by flow cytometry. The sample obtained prior to drug administration on C1D1 for each patient will serve as the baseline for that patient and follow-up samples will be compared back to that baseline. We will calculate the change from baseline for each patient and aggregate the data for all patients to look for common outcomes.

# 7.6.1.2 Apoptosis Markers

Apoptosis will be assessed at the time points listed on the Schedule of Events. See the lab manual or correlative specimen for collection, processing and storage instructions.

# 7.6.1.3 Minimal Residual Disease

At any time point in which a MRD specimen is required from the peripheral blood as according to the Schedule of Events two samples should be collected. One sample will be collected and analyzed as according to the institution's CLL flow cytometry MRD assay specifications. A second sample should be collected and processed for correlative studies. See the lab manual or correlative specimen for collection, processing and storage instructions.

# 7.6.2 Bone Marrow Aspirate

Any time a bone marrow biopsy is performed on this study after screening, at least two tubes of bone marrow aspirate will be collected for MRD testing. One sample will be collected and analyzed for CLL MRD by flow cytometry according to the institution's laboratory specifications. A second sample should be collected and processed for correlative studies. See the lab manual or correlative specimen for collection, processing and storage instructions.

Refer to the lab manual for sample collection and processing instructions.

# 7.6.3 Pharmacokinetic Studies

Plasma samples will be collected at defined time points in section 1.5.1 to assess the pharmacokinetics of RP-3500 and olaparib.

7.6.3.1 On C1D1 and C1D15, blood samples will be collected at pre-dose and 0.5, 1, 2, 4, and 24 hours post dose. Patients will take their doses of RP-3500 and olaparib in the infusion room or clinic after the pre-dose PK blood draw has occurred and at the instruction of the research team. For the 24 hour post dose collection, patients will have PK study blood drawn prior to taking their C1D2 and C1D16 drug doses.

7.6.3.2 On C1D8, blood samples will be collected at pre-dose, 0.5, 1, 2, and 4 hours post dose. Patients will take their doses of RP-3500 and olaparib in the infusion room or clinic after the pre-dose PK blood draw has occurred and at the instruction of the research team.

Blood samples will be processed to plasma and RP-3500 and olaparib will be analyzed by validated LC/MS-MS bioanalytical methods. PK parameters for RP-3500 and olaparib will be calculated using non-compartmental analysis: area under the concentration-time curve (AUC) from time 0 to last quantifiable concentration (AUC0-last); AUC from time 0 to infinity (AUC0-inf); maximum observed plasma concentration ( $C_{max}$ ); time to reach Cmax ( $T_{max}$ ) and terminal elimination half-life ( $t_{1/2}$ ). The effect of olaparib on the AUC0-last and AUC0-inf and Cmax of RP-3500 will be compared to respective monotherapy doses from other studies performed with RP-3500. RP-3500 and olaparib may also be analyzed using population PK methods.

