#### 2.3 Exploratory Objecti ves

2.3.1 To evaluate protein expression levels of  $\gamma$ H2AX, annexin V, cleaved PARP1 and cleaved caspase 3 during treatment with combination RP-3500 and olaparib as markers of DNA damage and apoptosis.

Exploratory Endpoint #1: Correlation of protein expression levels to best overall response and minimal residual disease status.

Exploratory Endpoint #2: Trend of protein expression levels at the beginning of therapy as compared to at the time of suspected relapse.

2.3.2 To assess the effects of combination of RP-3500 and olaparib on minimal residual disease status.

Exploratory Endpoint: Proportion of patients achieving undetectable minimal residual disease as assessed by either flow cytometry and/or next generation sequencing methods.

2.3.3 To determine the pharmacokinetic properties of combination RP-3500 and olaparib in relapsed/refractory chronic lymphocytic leukemia.

Exploratory Endpoint: Peripheral blood RP-3500 and olaparib concentrations when each are given at varying doses.

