# 6 STUDY INTERVENTION

### 6.1 Administration Schedule

Treatment will be administered on an outpatient basis. No investigational or commercial agents or therapies other than those described below may be administered with the intent to treat the patient's CLL.

Regimen Description					
Agent	Precautions	Dose	Route	Schedule	Cycle Length
RP-3500	Take with 8 oz of water at approximately the same times each day (±2 hours)	Capsule*	Oral	Once daily; intermittent weekly dosing of 2 days on and 5 days off	21 days (3
Olaparib	Take with 8 oz of water at approximately the same times each day (±2 hours)	Capsule*	Oral	Twice daily; intermittent weekly dosing of 2 days on 5 days off	weeks)
* Doses as appropriate for assigned dose level					

Study medications should be taken at approximately the same time every day. Study medication should not be crushed, chewed, or altered in any way. Subjects should not take extra medication for any reason nor should they re-administer in the case of vomiting after

administration. If a dose is missed outside of the dosing window, the dose should not be made up but rather dosing should continue at their regularly scheduled time.

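### Olaparib AUC0-last, AUC0-inf and half-life cannot be read by non-compartmental analysis from a 24 h sample that follows a second olaparib dose

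*Combined protocol and SAP*

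**What the plan says.** Objective 2.3.3 is exploratory: "To determine the pharmacokinetic properties of combination RP-3500 and olaparib in relapsed/refractory chronic lymphocytic leukemia". Its stated endpoint is the blood concentrations of the two drugs.

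Section 7.6.3 sets the sampling. For the two full-profile days: "On C1D1 and C1D15, blood samples will be collected at pre-dose and 0.5, 1, 2, 4, and 24 hours post dose". The last of these is a next-morning draw: "For the 24 hour post dose collection, patients will have PK study blood drawn prior to taking their C1D2 and C1D16 drug doses". For the middle visit: "On C1D8, blood samples will be collected at pre-dose, 0.5, 1, 2, and 4 hours post dose". The calendar in Section 1.5.1 gives the same times and adds C5D1, which stops at 2 h.

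Section 7.6.3 then states the analysis: "PK parameters for RP-3500 and olaparib will be calculated using non-compartmental analysis". One list serves both drugs: AUC0-last, AUC0-inf, Cmax, Tmax and terminal half-life. Population PK is mentioned for both drugs, as an option only.

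Section 6.1 sets the schedules. RP-3500: "Once daily; intermittent weekly dosing of 2 days on and 5 days off". Olaparib: "Twice daily; intermittent weekly dosing of 2 days on 5 days off". The diary in Appendix 3 has two olaparib time entries on each dosing day.

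**The concern.** A non-compartmental half-life or AUC0-inf is read from the tail of a single dose. For RP-3500, taken once daily, the 24 h sample is such a tail. For olaparib it is not: by the time of that draw the patient has taken an evening dose, about 12 h earlier if doses are evenly spaced. The sections on PK do not withhold that dose, fix its time, drop the 24 h sample for olaparib, or limit olaparib AUC to the first dosing interval.

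Applied as written, the method joins the 4 h point to a 24 h point made up largely of another dose. Olaparib would look longer-lived, and its total exposure from one dose larger, than they are. Section 4.2.3 lists PK, as available, among the data considered for the RP2D, so such values could come before the people making that decision.

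**Working it through.** The documents contain no PK figure to reproduce. The check asks what the stated method returns from the stated sampling times when the true answer is known.

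**Inputs from the documents**
- Sampling at 0, 0.5, 1, 2, 4 and 24 h (7.6.3, 1.5.1).
- Olaparib twice daily, RP-3500 once daily (6.1, Appendix 3).
- RP-3500 mean half-life 6.4 h (3.7.2). None is given for olaparib.

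**Assumptions**
- Olaparib half-life t from 3 to 15 h.
- Second dose equal to the first, at 12 h; also tried at 10 and 14 h.
- One-compartment oral model without noise, absorption rate 1 to 3 per h.
- Linear-up/log-down trapezoids; terminal slope from the last three points (2, 4 and 24 h).

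**Hand check, ignoring absorption**

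C4 = 2^(-4/t); C24 = 2^(-24/t) + 2^(-12/t); apparent half-life = 20 × ln 2 / ln(C4/C24).

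- t = 5 h: C4 = 0.574; C24 = 0.036 + 0.189 = 0.225. The evening dose supplies 0.189/0.225 = 84% of the 24 h concentration. Apparent half-life = 13.86 / ln(0.574/0.225) = 14.8 h.
- t = 10 h: C4 = 0.758; C24 = 0.189 + 0.435 = 0.625 after rounding. Apparent half-life is about 72 h.
- t = 15 h: C4 = 0.831; C24 = 0.330 + 0.574 = 0.904. The curve rises, so there is no half-life.

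**With absorption, second dose at 12 h (range over absorption rates)**

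| True half-life | Apparent half-life / true | AUC0-inf / true |
|---|---|---|
| 3 h | 2.4 to 2.6 | 1.65 to 1.77 |
| 5 h | 2.7 to 3.0 | 2.1 to 2.3 |
| 8 h | 3.8 to 4.9 | 3.2 to 3.9 |
| 12 h | 10 or more | 8.8 or more |
| 15 h | undefined (positive slope) | undefined |

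The timing of the second dose changes the size but does not remove the bias. At a true half-life of 5 h and absorption 1.5 to 3 per h, a second dose at 10 h gives a half-life 122 to 129% too long, and one at 14 h gives 243 to 259% too long.

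**Is the second dose the cause?** With it removed and everything else kept, the same sampling times recover the half-life within 0 to +12% and AUC0-inf within -3% to +3%. The sparse schedule alone does not produce the error.

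**Do other samples help?** C1D8 ends at 4 h and C5D1 at 2 h. On C1D1 and C1D15, dropping the 24 h point leaves 0 to 2 samples after the observed peak, and AUC0-4h covers 13 to 55% of the true AUC0-inf.

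**RP-3500.** No second dose falls inside its 24 h. At 6.4 h, linear-up/log-down trapezoids give AUC0-inf within about 1%. A plain linear rule overstates it by about 21%, because one straight line spans 4 to 24 h. Section 7.6.3 does not say which rule applies.

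**The case against.** The strongest case on the other side is about consequence. PK is exploratory and no primary or secondary endpoint uses it. The endpoint under 2.3.3 is concentrations, and these remain valid measurements. Olaparib Cmax and Tmax taken from 0-4 h come before the second dose. Section 4.2.3 uses PK only as available, beside safety and efficacy, and names no olaparib half-life or AUC. The data are not lost either: the diary records both dose times and population PK is already named. All of this stands, and it limits the weight of the point. It does not make the listed olaparib parameters correct, because the method that 7.6.3 commits to is the one that fails.

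The sizes also rest on assumed olaparib kinetics. That stands too: individual values are illustrative. The presence of a large bias is not, since it appeared throughout the range tried.

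A reader might infer more than the documents support:
- That the error distorts the assessment of olaparib's effect on RP-3500, or the starting-dose rationale in 3.11. The comparison with monotherapy in 7.6.3 is of RP-3500 parameters, and 3.11 concerns olaparib slowing RP-3500 metabolism. RP-3500 is once daily, so the evening olaparib dose does not enter its concentration curve as a second dose.
- That RP-3500 AUC0-inf and half-life are equally unusable. With a suitable trapezoid rule they are recovered well at the stated mean half-life. Late peaks would weaken the estimate in some patients, but the documents do not say how many.

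**Conclusion.** The concern holds for olaparib AUC0-last, AUC0-inf and half-life on C1D1 and C1D15 when the second dose is taken as scheduled. AUC0-last is included because its last point is the mixed 24 h sample. This is an error in the analysis as written, not a missing detail.

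For an assumed true half-life of 3 to 8 h, an equal second dose at 12 h and a one-compartment oral model, the half-life comes out about 2.4 to 4.9 times too long and AUC0-inf about 1.7 to 3.9 times too large; by 15 h neither can be computed. The existence of the error follows from the sampling and dosing sections alone; its size depends on these assumptions.

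It is worth correcting because the correction is cheap, but it touches only an exploratory objective. It does not show that the RP2D would be chosen wrongly. For RP-3500 the only residue is an unstated trapezoid rule.

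**What to change.** Reconcile the PK sampling in 7.6.3 and 1.5.1 with the twice-daily olaparib schedule in 6.1 by changing the analysis text of 7.6.3. No dosing change is proposed.

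1. Limit olaparib non-compartmental output to Cmax, Tmax and AUC0-4h, and exclude the 24 h sample from it. Label AUC0-4h as partial exposure.
2. Make population PK the planned method for olaparib instead of an option, using the diary time of each dose, including the evening one. Take olaparib AUC, clearance and half-life from that model. There the 24 h sample is useful, because the model knows about both doses.
3. As a minor addition, state linear-up/log-down trapezoids for RP-3500.

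The cost is wording, plus a commitment to a modelling step already foreseen. Fewer non-compartmental olaparib parameters would be reported, and the model-based values would rest on sparse late sampling, with nothing between 4 and 24 h, and on accurate diary times. No extra draw is needed. The 0.5 h draw should not be given up for a later one, since Section 3.7.2 puts the earliest RP-3500 Tmax at 0.5 h.

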# 7.7 Remote Visits/Telehealth

Some study visits and/or procedures may be conducted remotely in the following circumstances:

- Telehealth visits do not present an increased risk to the participant.
- All necessary data for the trial can be collected.
- Procedures do not include research related imaging, lab samples, and/or pathology which should be conducted in person.

The method of telehealth should be documented in the paricipants' charts.

# 8 ADVERSE EVENTS

8.1 Definitions

#### 8.1.1 Adverse events

21 CRF 312.32, ICH GCP, and OHRP define an adverse event as any untoward medical occurrence whether or not considered treatment-related. This definition extends to the worsening of any preexisting condition or symptom. All adverse events experienced during trial participation should be documented in the subject's research chart and corresponding eCRF

Laboratory abnormalities should not be listed as adverse events unless deemed clinically significant by the investigator or qualified designee. An abnormal test result or findings should not be recorded as an adverse event unless the following conditions are met:

- Associated with clinical symptoms; and/or
- Requires intervention (medical, surgical, or additional diagnostic testing); and/or
- Results in a change in study drug dosing; and/or
- Deemed by the investigator or qualified designee to be an adverse event.

While disease progression should be noted in the subject's research chart, it should not be reported as an adverse event.

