4.1 Justification for New Dosing Schema and Dose Escalation

At the previous dose level 1, five R/R CLL patients were treated with camonsertib (RP-3500) 40mg daily and olaparib 100mg BID dosed 3 days per week. One patient met the definition of a dose limiting toxicity due to persistent grade 4 thrombocytopenia lasting  $\geq$ 7 days. Cytopenias were the most common AEs with 2/5 (40%) of patients experiencing grade 4 thrombocytopenia as per the iwCLL criteria. Grade  $\geq$ 3 neutropenia occurred in 2/5 (40%) of patients with one patient experiencing a grade 3 neutropenic fever outside of the DLT window.

In the ongoing parallel ATTACC study (NCT04972110) of combination camonsertib (RP-3500) and PARPi combinations (either niraparib or olaparib) in patients with molecularly selected cancers (i.e. DDR-deficient solid tumors), similar cytopenias were observed with the 3 days per week dosing. However, better tolerance of the combination was observed when patients were dosed only 2 days per week. In preliminary data, reduction of the dosing to 2 days per week significantly reduced ≥grade 3 toxicities by 5-fold as compared to 3 days per week dosing at similar dosages of combination RP-3500 and olaparib. The 2/5 (i.e. 2 days on and 5 days off) dosing strategy is supported by previous preclinical data generated in DDR-deficient bladder cancer cell lines in which shortening the treatment of the cells to 48 hours had no significant effect on the IC50 as compared to continuous dosing (Refer to RP-3500 Investigator Brochure Section 4.2.1.4.2.1). Furthermore, treating various DDR-deficient solid tumor cell lines with RP-3500 and various PARPi dosed with a 2/5 strategy in vitro demonstrated strong synergy with the combination treatments (Refer to RP-3500 Investigator Brochure Section 4.2.1.5.1). Given the prior clinical experience of RP-3500 and olaparib with the 2/5 dosing strategy in solid tumor patients along with the existing preclinical data to support this dosing method, we propose to amend the phase Ib of combination RP-3500 and olaparib in R/R CLL patients to be dosed with a 2/5 treatment strategy to improve the tolerability of the combination.

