### 6.6.3 Hematologic and Infectious Toxicities

Optimal supportive care should be offered to the patient in order to mitigate toxicities. Where appropriate, this includes administration of G-CSF, GM-CSF and blood/platelet transfusions as per institutional guidelines. At the start of each cycle, hold therapy until ANC  $\geq$ 500/mm^3 and platelet count is  $\geq$ 25,000/mm^3. Lymphopenia is an expected toxicity of CLL treatments and therefore should be graded and recorded as per CTCAE v5.0, but treatment holds and dose changes are not needed.

This study will utilize the 2018 IWCLL grading scale for hematologic adverse events in patients with baseline platelet count <100,000/mm^3 and/or baseline hemoglobin less than the lower limit of normal. Grading of ANC is at the nadir within the cycle, and patients who have an ANC <1 x  $10^{9}$ /L before therapy will not be evaluable for toxicity. These criteria account for baseline cytopenias secondary to CLL and are detailed in Table 12 below.

Grade	Decrease in platelets or hemoglobin from baseline value, %	Absolute neutrophil count* (nadir) x 10  /L
0	No change to 10	≥2
1	11-24	≥1 and <2
2	25-49	≥1 and <1
3	50-74	≥0.5 and <1
4	≥75	<0.5

Table 12. iwCLL Hematologic Grading

\*If the absolute neutrophil count (ANC) reaches  $<1 \times 10^{9}$ /L, it should be judged to be grade 3 toxicity. Other decreases in the white blood cell count or in circulating granulocytes are not to be considered because a decrease in the white blood cell count is a desired therapeutic end point. A gradual decrease in granulocytes is not a reliable index in CLL for stepwise grading of toxicity. If the ANC was  $<1 \times 10^{9}$ /L before therapy, the patient is not evaluable for toxicity referable to the ANC. The use of G-CSF is irrelevant for the grading of toxicity, but should be documented.

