The order in which dose reductions will occur will be change in dosing schedule (Table 10.: Dosing Schedule Modifications) with either sequential (preferred) or concurrent changes in drug dosages (Table 11). If drug dosage changes are required, the order in which dose reductions will occur will be camonsertib (RP-3500) first followed by olaparib if the AE continues to occur. If at any time a dose reduction would leave camonsertib (RP-3500) or olaparib doses less than DL 1 (Table 11. Dose Reduction Levels), the patient will be taken off protocol. Treatment delays for adverse events exceeding 21 days will lead to protocol removal. If reduction of the dosing schedule and/or drug doses resolves the patient's toxicity to grade  $\leq 1$  for at least 3-6 weeks, increasing camonsertib (RP-3500) and/or olaparib back to the prior dose or dosing schedule is permitted after discussion with the study PI.

Event Name	Neutropenia	
Grade of Event	Management/Next Dose for RP - 3500	Management/Next Dose for Olaparib
≤ Grade 1	No change in dose	No change in dose
Grade 2	No change in dose	No change in dose
Grade 3	No change in dose	No change in dose
Grade 4	Hold until ANC ∫ is ≥1000/mm  . G- CSF administration is recommended. At first occurrence, no change in dose or dosing schedule. If toxicity recurs, follow reductions in dosing schedule and drug dosages as per sections 6.6.1 and 6.6.2 only if grade 4 neutropenia lasts ≥7 days with optimal supportive care.	Hold until ANC ∫ is ≥1000/mm  . G- CSF administration is recommended. At first occurrence, no change in dose or dosing schedule. If toxicity recurs, follow reductions in dosing schedule and drug dosages as per sections 6.6.1 and 6.6.2 only if grade 4 neutropenia lasts ≥7 days with optimal supportive care and

Table 13. Management and dose modification guidelines for hematologic toxicities encountered with combination camonsertib (RP-3500) and olaparib.

6.6.2 if RP-3500 dosage already

		RP-3500 dosage already decreased for the same toxicity.	
j Only for patients with ANC $\geq$ 500/mm 	 Only for patients with baseline ANC $\geq$ 1000. For patients with baseline ANC <1000, hold until ANC $\geq$ 500/mm 		
Event Name	Thromboc	ytopenia	
Grade of Event	Management/Next Dose for RP - 3500	Management/Next Dose for Olaparib	
≤ Grade 1	No change in dose	No change in dose	
Grade 2	No change in dose	No change in dose	

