## 9.5 Secondary Endpoints

#### 9.5.1 Safety and Tolerability

All subjects who receive any study treatment will be included in the final summaries and listings of safety data. The detailed information collected for each AE will include a description of the event, duration, severity, relatedness to study drugs, action taken, and clinical outcome. The severity of the AEs will be graded according to the CTCAE v5.0. The statistical analysis of the safety data will be descriptive and tabular.

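### Recording of uncomplicated grade 3 neutropenia as an adverse event is left to investigator discretion, sits uneasily with section 6.6.3, and has no laboratory-based table behind it

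*Combined protocol and SAP*

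**What the plan says.** **Recording rule (8.1.1).** The section opens with the default that "Laboratory abnormalities should not be listed as adverse events unless deemed clinically significant by the investigator or qualified designee". It continues: "An abnormal test result or findings should not be recorded as an adverse event unless the following conditions are met". Four conditions follow, joined by and/or: clinical symptoms, a need for intervention (further diagnostic testing included), a change in study drug dosing, or "Deemed by the investigator or qualified designee to be an adverse event".

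**Management of neutropenia (6.6.3).** For both drugs, the grade 3 row of Table 13 reads "No change in dose". The cycle-start rule, "At the start of each cycle, hold therapy until ANC", uses a threshold of 500/mm³, so a grade 3 value does not trigger it. G-CSF is offered where appropriate. Section 6.8 strongly recommends it when ANC below 1,000/µL is expected to last at least 7 days.

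**Grading (6.6.3).** The note to Table 12 makes an ANC below 1 × 10⁹/L a grade 3 toxicity, and the text sets the grade at the cycle nadir. Lymphopenia "should be graded and recorded as per CTCAE v5.0, but treatment holds and dose changes are not needed".

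**Analysis (2.2.1, 9.5.1).** The safety endpoint is the frequency of AEs and SAEs. Section 9.5.1 lists the details collected for each AE, says "The severity of the AEs will be graded according to the CTCAE v5.0", and plans descriptive tables. It names no worst-grade or shift table of laboratory values.

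**Earlier experience (4.1).** At the previous dose level 1, grade 3 or higher "neutropenia occurred in 2/5 (40%) of patients".

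**The concern.** Section 4.1 calls cytopenias the most common adverse events, and they prompted the change to two days of dosing per week. A reader of the results will want the neutropenia rate at each dose level. Under 4.2.3 the RP2D is chosen on cumulative safety as well as on DLTs, so that rate can bear on the choice.

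Section 6.6.3 treats an ANC of 500-999/mm³ as grade 3 by its value. Section 8.1.1 then makes entry of that value in the adverse event data depend on whether someone judges it significant. There are two institutions (5.7), and they may judge differently. If an event is left out, no other planned summary would show it: uncomplicated grade 3 neutropenia is not a DLT, and the stopping rule counts non-hematologic events only.

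**Working it through.** **Step 1. Which values fall to discretion?** Take an afebrile patient with ANC 500-999/mm³ who receives no treatment for it, and apply the four conditions of 8.1.1.

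| Condition in 8.1.1 | Met? | Source |
|---|---|---|
| Symptoms | No | by assumption |
| Intervention | No, unless G-CSF, antibiotics or extra testing is given | 6.6.3, 6.8 |
| Dosing change | No | Table 13; cycle-start hold applies only below 500/mm³ |
| Judged an AE | At discretion | 8.1.1 |

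Only the last route is left. Table 13 holds both drugs for grade 4 neutropenia, grade 3-4 thrombocytopenia and neutropenic fever, so those would ordinarily meet the dosing or intervention condition. The exposed group is therefore narrow: uncomplicated, untreated grade 3 neutropenia, together with lymphopenia that causes no symptoms.

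**Step 2. Which results can be affected?**
- *DLT rate:* not affected. With baseline ANC of at least 1,000/mm³, the neutrophil DLT needs ANC below 500/mm³ for at least 5 days despite support. With a lower baseline it needs a fall of at least 75%, which puts ANC below 0.25 × 1,000 = 250/mm³.
- *Stopping rule (9.3):* not affected; non-hematologic events only.
- *ORR:* not affected.
- *AE frequency (2.2.1, 9.5.1):* affected.

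**Step 3. The plan's own figure.** 2/5 = 0.40. The exact two-sided 95% interval (Clopper-Pearson) is 5.3% to 85.3%.

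**Step 4. Illustration of size.** Let s be the share of grade 3 or higher neutropenia that is uncomplicated, untreated grade 3, and c the probability that such an event is recorded. Neither is in the documents; both are assumptions.

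Recorded rate = 0.40 × [(1 − s) + s × c]

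| s | c = 0 | c = 0.5 | c = 1 |
|---|---|---|---|
| 0.25 | 30% | 35% | 40% |
| 0.50 | 20% | 30% | 40% |
| 0.75 | 10% | 25% | 40% |

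For example, s = 0.75 and c = 0 give 0.40 × 0.25 = 10%. In 24 patients the range is 24 × 0.10 = 2.4 to 24 × 0.40 = 9.6 patients. A table built from the ANC values corresponds to c = 1 and gives 40% whatever s is, provided the low value was sampled.

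**Step 5. Effect of one omission.** Section 4.2.3 allows about 3 to 12 patients per dose level. One unrecorded patient lowers the rate by 1/3 = 33 points at n = 3, 1/12 = 8 points at n = 12, and 1/24 = 4 points in the full expansion cohort.

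**The case against.** Five points can be made for the plan as written.

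1. *Nothing is forbidden.* A reader might infer that 8.1.1 bars these values from the record. It does not: the fourth condition is enough alone. This stands; the defect is discretion, not prohibition.
2. *A dose instruction is not an instruction to do nothing.* A reader might take Table 13 to mean that grade 3 neutropenia calls for no action. The row concerns dose only. G-CSF, antibacterial prophylaxis or additional testing prompted by the value could each make the event recordable. This stands and narrows the exposed group, but short or untreated episodes remain in it.
3. *The lymphopenia passages need not contradict each other.* A reader might see a flat contradiction between 6.6.3 and 8.1.1. The specific instruction can be read as taking precedence, with the fourth condition accommodating it. Section 6.6.3 also calls lymphopenia expected. The texts are better described as unreconciled, but the site still has to work out which applies.
4. *No comparison between schedules is planned.* A reader might infer that a lower neutropenia rate on the new schedule would be an artefact. Section 9.1.1 excludes the five earlier patients from the analysis, and nothing shows that recording would differ between schedules. That inference is not supported.
5. *Laboratory summaries are not ruled out.* Section 9.5.1 speaks of summaries and listings of safety data, and 7.2.3 refers to safety laboratory tests. True, but no laboratory table is named, and the stated endpoint is AE frequency.

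The illustrative range is also open to attack. Section 4.1 mentions one neutropenic fever alongside the two neutropenia cases. If that patient is one of the two, at most half were uncomplicated, and the range at s = 0.5 is 20-40%. Two patients cannot fix s either way.

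**Conclusion.** The concern holds in a limited form. Under 8.1.1 an afebrile, untreated grade 3 neutropenia is recorded only at the investigator's discretion, while 6.6.3 grades it from the laboratory value. With no laboratory table named in 9.5.1, the descriptive rates of grade 3 or higher neutropenia and of lymphopenia can be too low and can vary by site.

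The consequence is confined to a descriptive secondary endpoint and to whatever weight those rates carry in the RP2D discussion. The 10-40% range shows only how far discretion could move a rate. It rests on a 2/5 estimate and on assumed values of s (0.25 to 0.75) and c (0 to 1), and should not be quoted as an expected bias. The change is worth making because cytopenia is the regimen's most common toxicity and the needed CBCs are already required.

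**What to change.** **Section 9.5.1.** Add a table of worst post-baseline grade, and shift from baseline, for ANC, platelets, hemoglobin and lymphocytes. Derive it from all available scheduled and unscheduled CBCs, whether or not an AE was recorded. State the scale: that of 6.6.3 and 8.2 (iwCLL where it applies for baseline cytopenias, otherwise CTCAE v5.0), with patients whose baseline ANC is below 1 × 10⁹/L shown as not evaluable for ANC, as 6.6.3 specifies.

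**Section 8.1.1.** Add one sentence exempting grade 3 or higher hematologic values and lymphopenia from the non-recording default, so that it agrees with 6.6.3.

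**Cost.** One extra table and one sentence. Section 11.1 says only that relevant source data go into the eCRF, so capture of every CBC value must be confirmed. Reported cytopenia rates may rise. The table will not catch everything: the Schedule of Events has CBCs on days 1, 8 and 15 of cycle 1 and days 1 and 8 of cycle 2, but on day 1 only from cycle 3, so nadirs between visits can still be missed.
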